2. STUDY PROCEDURES

a. Procedures

We will recruit a total of 30 outpatient participants for an open label pilot study (aged 18-80 years old) using intermittent theta burst stimulation (iTBS) over the left dorsolateral prefrontal cortex (LDLPFC) and right dorsolateral prefrontal cortex (RDLPFC) (up to five days, up to 10x/day) with the MagPro rTMS System. Participants will be required to meet diagnostic criteria for Bipolar I or Bipolar II (without psychosis or rapid cycling), in a current depressive episode. History related to participant's mood cycle will be obtained to ensure treatment is delivered during a depressive cycle which will be expected to span beyond the length of the 5-day treatment period based on the participant's most recent depressive episode duration. Psychiatric history will be obtained through each participant's psychiatric provider records to confirm diagnosis and bipolar symptom cycle history, which will be reviewed and confirmed during screening.

Participants will be excluded if they have been hospitalized within the last 6 months due to suicidality, depression severity or hypomania.

Participants will be required to have stabilized on medications (including at least one of the following as a mood stabilizer Lithium with a level of at least 0.6, Depakote with a level of at least 50, or a therapeutic dose of carbamazepine, oxcarbamazepine, or an antipsychotic) without dose changes for at least 6 weeks prior to the active study time period.

They will be ruled out if they have had a manic episode in the past year or a hypomanic episode in the last 6 months.

Participants will be asked to stay on their psychotropic medications for stabilization throughout the screening, baseline, and active study time periods. Participants will be required to have an established psychiatric prescriber.

We will use an adapted baseline covariate of the Maudsley Staging Method for TRD bipolar depression.

The study will have 4 time-periods:

- screening time period
- baseline time period
- active study time period

- follow-up time period

We will utilize a modified study design version of Williams (2018) and Cole et al (2020)

Reference: Cole EJ, Stimpson KH, Bentzley BS, et al. Stanford Accelerated Intelligent Neuromodulation Therapy for Treatment Resistant Depression. Am J Psychiatry. 2020;177(8):716-726.

doi:10.1176/appi.ajp.2019.19070720

Study Visit Schedule

Pre-screening	Screening Visit 1 Remote	Baseline visit2	Day1-5 Visit 3-7	Immediate Post) (Tuesday-Wednesday) Visit 8	Self-reports (Post 2,3week)	Post 4 week Visit 10 Remote visit (optional) Self-report(requirement)
Consent						
Initial screen consent	Screening consent	Study consent form Capacity consent				
Clinician Administered Assessments / Scales						
Demographic	Stanford demo					
Demographic II	inclusion/exclusion					
Dx - Psychiatrist - Tx Hx	MRI safety TASS (TMS safety) BSL- 23(borderline)	MT	aTBS checklist			
Med & Psych Hx	Med Med & Psych	Self-report Mx review	Concomitant Mx review			

	Hx ATHF-current ATHF-lifetime	Concomitant Mx review				
Depression Sx - IDS-SR	Mausley+Thase Rush		randomization			
Mania Sx - Past - Current - Med	SCID-including BPD module MINI					
Psychotic Sx - Lifetime		UTox UPreg	UTox	UTox		
		COVID-19 screening	COVID-19 screening	COVID-19 screening		
Self-questionnaire						
	MADRS-S GAD-7	MADRS-S PHQ-8 GAD-7 BSS	MADRS-S-24h PHQ-8 BSS	PHQ-8 MADRS-S GAD-7 BSS	PHQ-8 (2,3w)	PHQ-8 MADRS-S GAD-7
Clinician rating						
Scanning safety	MADRS-C HAMD-17	MADRS-C HAMD-17	HAMD-6 YMRS	YMRS MADRS-C		MADRS-C HAMD-17

	YMRS	YMRS		HAMD-17		YMRS
Mx						
- MS	CSSRS	MSSI		MSSI		MSSI
- SSRI	MSSI					
- SNRI						
- TCA						
- MAOi						
- APx						
- AED						
- Thyroid						
- BB						
- Amphetamine						
- MPH						
- Nonstimulant						
- Antianxiety						
- Insomnia						
- other						
		CGI-S		CGI-S		CGI-S
				CGI-I		CGI-I
OTHER Self reports						
	Holmes & Rahe Stress					
	PSQI					
	SHAPS	SHAPS		SHAPS		SHAPS
		CTQ				

		Self-criticism scale					
Other measure							
		Resting EEG		Resting EEG			
			Adverse events				
			HRV				
		Resting state fMRI connectivity		Resting state fMRI connectivity			
		T1 anatomical		T1 anatomical			
		DWI		DWI			

b. Procedure Risks

These methods are the least risky because the intervals of stimulation have been shown to be appropriate for theta burst stimulation in the motor system with no adverse outcomes. The addition of R-DLPFC iTBS should provide an additional safety measure for the risk of hypomanic/manic conversion, although this risk is low. Additionally, all speech samples used for analyses will be based on randomly segmented splices of audiotapes; further, the 5-minute speech sample requires participants to answer a set of standardized questions without any reference to personal information.

c. Use of Deception in the Study

No deception will be used.

d. Use of Audio and Video Recordings

Video and Audio Recordings:

We will be video and audio recording study participants during the clinical assessments conducted with them while enrolled in the study. The video and audio recordings will be recorded using Zoom video from an encrypted Stanford owned laptop. The recordings will be available for training purposes for study personnel only or as otherwise consented to on the consent form. We will not use or distribute the recordings to outside personnel or scientific meetings etc. unless directly indicated by the participant on the consent form.

e. Alternative Procedures or Courses of Treatment

Participants with insurance could alternatively receive traditional rTMS, although not all insurance companies consider bipolar TRD to be covered under the FDA approved guidelines.

f. Will it be possible to continue the more (most) appropriate therapy for the participant(s) after the conclusion of the study?

The participants will have the option of pursuing treatment as usual after the study (medications, therapy, traditional rTMS).

g. Study Endpoint(s)

The study will be terminated if either:

- a) 6 participants reach hypomania as defined by a score of greater than 10 on the YMRS scale or
- b) if 2 participants meet DSM-5 clinical criteria for mania without resolution after switching to full right sided DLPFC treatment within 24 hrs.

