Our recent pilot study utilized prior evidence to further enhance the propensity of antidepressant response to iTBS by modifying parameters in pulse spacing, dosage and treatment target location (Cazzoli et al., 2012; Fox et al., 2012; Gamboa, Antal, Moliaidze, & Paulus, 2010; Noh, Fuggetta, Manganotti, & Fiaschi, 2012; Nyffeler, Cazzoli, Hess, & Muri, 2009). Applied in a small pilot sample of individuals with unipolar (n=20) and bipolar (n=5) TRD, the use of an accelerated iTBS paradigm yielded approximately 90% response and remission rates in depressive symptoms, in both unipolar and bipolar TRD patients (Cole et al., Manuscript in preparation). Of the 5 bipolar TRD patients, all met depression remission criteria within 5 days of treatment, with no hypomania/mania conversion observed during treatment or at follow-up. This study aims to further explore the use of an adapted accelerated iTBS protocol for bipolar TRD.

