If the participant displays an increased YMRS score (>=2 points) on 2 questions, stimulation will be switched to all right sided treatment to prevent any possibility of further inducing hypomania or mania. If these symptoms persist or increase to any greater degree during that same treatment series, the patient will be treated with Ativan and their primary psychiatrist will be contacted by the PI. If any of the research team or clinical staff believe that the participant may be showing signs of hypomania/mania, the YMRS will be administered by trained personnel immediately, the researchers will not wait until the daily assessments are conducted.

d. Study Conclusion

The experiment will terminate when the final participant has completed their treatment and all data has been analyzed.

e. Data Safety Monitoring Plan (DSMC)

i. Data and/or events subject to review

Adverse events, protocol deviations, aggregate data will all be frequently reviewed by the Study PI and Protocol Director (PD).

ii. Person(s) responsible for Data and Safety Monitoring

The Principal Investigator and Protocol Director

iii. Frequency of DSMB meetings

N/A

iv. Specific triggers or stopping rules

If there is evidence of significant risk to the participants such as multiple seizure events or worsening of psychiatric state in more than 20% of the participants.

v. DSMB Reporting

N/A

vi. Will the Protocol Director be the only monitoring entity? (Y/N)

Yes

vii. Will a board, committee, or safety monitor be responsible for study monitoring?
(Y/N)

No

f. Risks to Special Populations

N/A

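### Stopping rule 2g(b) counts mania towards its limit of 2 only after a failed switch to right-sided stimulation, so on its natural reading mania starting after the last session cannot count

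*Protocol*

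**What the plan says.** Section 2g of the Protocol gives two fixed limits, either of which ends the study.

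- 2g(a): "6 participants reach hypomania as defined by a score of greater than 10 on the YMRS scale". It has no condition on treatment and no time window.
- 2g(b): "if 2 participants meet DSM-5 clinical criteria for mania without resolution after switching to full right sided DLPFC treatment within 24 hrs".

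Section 2a sets the stimulation course at "up to five days, up to 10x/day". Section 6c says when stimulation moves to the right side only (a rise of at least 2 points on two YMRS questions) and what follows: "If these symptoms persist or increase to any greater degree during that same treatment series", the participant receives Ativan and the investigator contacts the psychiatrist.

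Section 6e.iv adds a general trigger: "evidence of significant risk to the participants such as multiple seizure events or worsening of psychiatric state in more than 20% of the participants". There is no monitoring board, and the Protocol Director is the only monitoring entity (6e.vi and 6e.vii).

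After treatment, the visit schedule lists the YMRS at the immediate post-treatment visit and in the column headed "Post 4 week Visit 10 Remote visit (optional) Self-report(requirement". Weeks 2 and 3 list only the PHQ-8.

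**The concern.** Mania/hypomania is the first risk that section 6a names for rTMS, and 2g(b) is the only fixed stopping limit specific to full mania. Its count depends on a rescue step that exists only while stimulation is being given. The Protocol does regard conversion after treatment as relevant: section 3a reports the five bipolar pilot patients "with no hypomania/mania conversion observed during treatment or at follow-up", and the schedule measures YMRS after the course has ended.

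The two limits therefore diverge once treatment stops. Late hypomania counts fully towards its limit of 6. Late full mania, the more serious event, can be only one of those 6 and never one of the 2. With no independent board, the fixed limits carry more of the safety burden than they otherwise would.

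**Working it through.** **The wording**

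1. 2g(b) requires mania that has not resolved after a switch to right-sided treatment. The 24-hour phrase may attach to the switch or to the resolution. On either reading a switch must have taken place.
2. Section 6c makes the switch a change to stimulation in progress, within one treatment series.
3. Stimulation ends by day 5, and no section provides right-sided sessions afterwards.
4. So mania with onset after the last session cannot meet the condition in 2g(b).

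**What still applies to late mania**

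- 2g(a), if a YMRS above 10 is recorded. The case joins all other participants above 10, whatever the timing. If four others have already exceeded 10, two late cases bring the count to 4 + 2 = 6 and end the study without discretion.
- 6e.iv, as a matter of judgement. If its 20% example is read against those treated so far, two cases exceed it only up to n = 9 (2/9 = 22.2%; 2/10 = 20.0%). At n = 30 it takes 7 (6/30 = 20.0%).
- 6c, which has the psychiatrist notified at once of signs of hypomania/mania. This is not limited to treatment days, but it is not a stopping rule.

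**Illustration of size**

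The limit of 2 is stated without a derivation, so there is no figure to reproduce. N = 30 comes from section 2a. The late-mania rate p is an assumption. The bipolar pilot's 0 of 5 gives a one-sided 95% upper bound of 1 − 0.05^(1/5) = 45%, so it excludes none of the values used.

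With X ~ Binomial(30, p), P(X ≥ 2) = 1 − (1−p)^30 − 30p(1−p)^29. At p = 5% this is 1 − 0.2146 − 0.3389 = 0.446.

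| Assumed p | P(X ≥ 2) | P(X ≥ 6) |
|---|---|---|
| 2% | 12% | 0.003% |
| 5% | 45% | 0.3% |
| 10% | 82% | 7% |

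The last column fills the 6 with late mania alone, so it overstates the contrast. Suppose instead that a further 10% of participants exceed YMRS 10 for other reasons (also an assumption), with p = 5%:

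- As written, through 2g(a): P(Binomial(30, 0.15) ≥ 6) = 29%.
- With late mania also counted towards 2, the study continues only with no late case and at most 5 others, or one late case and at most 4 others. Given no late case on a participant, the chance of another excess is 0.10/0.95. The stopping chance is 1 − 0.2146 × 0.9109 − 0.3389 × 0.8158 = 53%.

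The difference falls from about 44 points (44.6% − 0.3%) to 24 points (52.8% − 28.9%).

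If 6e.iv is instead applied as a running rule of more than 20% of those treated so far, alongside the limit of 6 and with late mania alone counted, the current text stops with probability 21% at p = 5% and 44% at p = 10% when applied from the first participant. Applied from the fifth, the figures are 8% and 29%. All are below the 45% and 82% for a limit of 2.

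**The case against.** A reader might infer that late mania escapes every stopping rule, or that two late episodes can end the study only if the investigators choose to invoke the general clause. The documents support neither: 2g(a) counts such cases once a YMRS above 10 is recorded and can be completed by them, 6e.iv is open-ended, and the notification duties in 6c have no time limit.

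Four further objections deserve an answer.

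- *2g(b) could be read as an exemption, so that mania counts unless a switch resolves it.* This is possible but strained, because the sentence makes non-resolution after a switch part of what is counted.
- *The condition has a rationale.* Section 3a describes right-sided stimulation as effective for mania, and section 2b calls it a safety measure against conversion. A limit on mania that the rescue fails to control is coherent during treatment. It gives no reason to omit mania for which the rescue was never available, and 2g(a) does not follow the same logic.
- *The duty to administer the YMRS on suspicion covers late cases.* Section 6c says "the researchers will not wait until the daily assessments are conducted". That points to treatment days, though no window is stated. A YMRS result would in any case feed the limit of 6, not the limit of 2.
- *The probabilities overstate the benefit.* This stands. The 6 is shared with other cases. Some limits would also be reached too late to protect many participants: the chance of 2 cases within the first 20 is 6%, 26% and 61% at rates of 2%, 5% and 10%. The Protocol names no unacceptable rate, so the figures do not show which stops would be right.

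**Conclusion.** The point holds in a limited form. On its natural reading 2g(b) cannot count mania that starts after the last session, and this sits badly beside 2g(a), which counts hypomania at any time. The conclusion rests on the wording of 2g(b), the description of the switch in 6c and the five-day course, and on no assumed rate.

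The size is uncertain. The figures of 45% against 0.3% at a 5% rate are illustrative and mark the wide end of the contrast. With a further 10% of participants above YMRS 10, it is 53% against 29%. These calculations assume 30 independent participants and a recorded YMRS above 10 for every late case. They leave out mania during treatment that already counts under 2g(b), and, except in the running-rule figures, they assume 6e.iv is not invoked. Because other safeguards partly cover late mania, the severity is minor to moderate.

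**What to change.** Add one sentence to 2g(b): DSM-5 mania that starts after the last stimulation and up to the 4-week follow-up, confirmed by the investigator and including cases reported by the participant's psychiatrist, counts towards the limit of 2 without the switch condition. Leave 2g(a) and 6e.iv as they are.

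The cost is protocol wording, a reporting route from the psychiatrist whom inclusion criterion 8 already requires, and confirmation of each reported case. No participants or scheduled visits are added. The downside is some added early stopping, including for spontaneous episodes that a single-arm study cannot separate from treatment effects. If late mania truly occurred in 2% of participants, the limit of 2 would be reached with probability 12%.

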3. BACKGROUND

a. Past Experimental and/or Clinical Findings

Bipolar disorder (BD) is an episodic illness comprised by periods of disabling depressive, elevated and/or mixed mood states, affecting approximately 4.8% of adults each year (Merikangas, et al., 2011; Miller, Dell'Osso, & Ketter, 2014). Individuals with BD are more impacted by symptoms of depression than mania or mixed symptoms; however, antidepressant medications remain controversial due to the potential concern of manic or hypomanic conversion (Judd et al., 2003; Thase, 2005; Tondo, Isacsson, & Baldessarini, 2003). Compared to the general population, individuals with BD are at greater risk to attempt (1:3) and complete (1:20 to 1:40) suicide, with a greater risk among those experiencing longer periods of depression than manic states (Baldessarini et al., 2006; Leverich et al., 2006). Not only are first line treatments limited in BD, but treatment resistance can be up to two times higher when compared to unipolar depression (Li et al, 2012; Tondo et al., 2014). Despite some advances in recent decades with the use of pharmacologic and psychotherapeutic interventions for bipolar disorder symptoms, few treatment modalities allow for both phases of symptom clusters (depressive and mania/hypomania) to be treated (Geddes & Miklowitz, 2013).

Repetitive transcranial magnetic stimulation (rTMS) is a safe, neuromodulator clinical tool utilized in the treatment of depression, which when applied to the left dorsolateral prefrontal

cortex (LDLPFC) has shown to be safe and effective in treating individuals with both unipolar and bipolar depression (Rachid, Moeglin & Sentissi, 2017; Rostami, et al., 2017; Tavares et al., 2017). Additional studies have shown that high frequency rTMS over the RDLPFC is effective in treating symptoms of bipolar mania (Grisaru, Chudakov, Yaroslavsky and Belmaker, 1998; Praharaj, Ram and Arora, 2009; Saba et al., 2004). Intermittent theta burst stimulation (iTBS) is a form of patterned rTMS, recently deemed "non-inferior" to standard rTMS in the treatment of unipolar major depressive disorder (MDD) (Blumberger et al., 2018; Chung, Hoy, & Fitzgerald, 2015). With a significant benefit in reduced treatment time in iTBS (10 minutes daily) compared with the standard rTMS treatment time (40 minutes daily) for 4-6 weeks, time constraints, transportation, and the financial resources to attend daily sessions over weeks of time remain cumbersome limitations (Bakker et al., 2015). Accelerated rTMS has recently been explored to determine the safety, tolerability, and efficacy in delivering multiple sessions over fewer days, to achieve a similar outcome compared with a standard series of rTMS (Sonmez et al., 2018). Reducing treatment time is important not only to reduce the individual time and resource strain, but also to address accelerating antidepressant response in more severely depressed individuals, at greater risk for suicide. Despite advancements in the clinical use of rTMS for depression, individual variation, and extensive burden of resources over time require further development. As individuals with bipolar disorder tend to have more treatment resistance with more time in depression and at greater risk for suicide, the development of symptom cluster targeting, non-invasive treatment options are of great importance.

Our recent pilot study utilized prior evidence to further enhance the propensity of antidepressant response to iTBS by modifying parameters in pulse spacing, dosage and treatment target location (Cazzoli et al., 2012; Fox et al., 2012; Gamboa, Antal, Moliaidze, & Paulus, 2010; Noh, Fuggetta, Manganotti, & Fiaschi, 2012; Nyffeler, Cazzoli, Hess, & Muri, 2009). Applied in a small pilot sample of individuals with unipolar (n=20) and bipolar (n=5) TRD, the use of an accelerated iTBS paradigm yielded approximately 90% response and remission rates in depressive symptoms, in both unipolar and bipolar TRD patients (Cole et al., Manuscript in preparation). Of the 5 bipolar TRD patients, all met depression remission criteria within 5 days of treatment, with no hypomania/mania conversion observed during treatment or at follow-up. This study aims to further explore the use of an adapted accelerated iTBS protocol for bipolar TRD.

4. DEVICES USED IN THE STUDY

a. Investigational Devices (Including Commercial Devices Used Off-Label)

Investigational Device 1	
Name:	MagPro X100
Description:	Transcranial Magnetic Stimulation Device with theta burst stimulation
Significant Risk? (Y/N)	No
Rationale for Non-Significant Risk	
The 'traditional 10Hz TMS' is on label and the theta burst stimulation is off label. It is the same device for both. The Magventure is about to be approved by the FDA for depression in 2 weeks. When that happens, the 'traditional 10Hz' stimulation will be on label with an approved device. The theta burst stimulation is minimal risk because the risk of seizure is very low (only reported once in literature) and there is no other risk other than minimal scalp irritation. We will be using an approved device 'off label' stimulation parameters which has a lower risk profile than the on label approved parameters.	
Investigational Device 2	
Name:	Lucus Center MRI (GE)

Description:	It is a non-invasive imaging scanner. Some of the radio frequency imaging coils, imaging software and devices being used in the scan are not approved by the FDA but are similar to counterparts that have been approved by the FDA. There are currently no known harmful side-effects associated with temporary exposure to the strong magnetic field used by MRI scanners. There is a small risk of heating from the cables associated with these devices. However, they do not pose a serious risk to the health, safety, or welfare of a subject.
Significant Risk? (Y/N)	No
Rationale for Non-Significant Risk	We will be using the exact same MRI device at the Lucas Center as we have been using at the CNI. The CNI is closing for 3 months for renovations, and to keep the study moving forward, we will use the same device at the Lucas Center.
Investigational Device 3	
Name:	3T UHP
Description:	It is a non-invasive imaging scanner. Some of the radio frequency imaging coils, imaging software and devices being used in the scan are not approved by the FDA but are similar to counterparts that have been approved by the FDA. There are currently no known harmful side-effects associated with temporary exposure to the strong magnetic field used by MRI scanners. There is a small risk of heating from the cables associated with these devices. However, they do not pose a serious risk to the health, safety, or welfare of a subject.
Significant Risk? (Y/N)	No
Rationale for Non-Significant Risk	The 3T Ultra-High Performance (UHP) MRI scanner from GE is an upgrade to the 3T MR750 which was a commercial FDA-approved system. The UHP system utilizes many components from GE's 3T Signa Premier, including gradient drivers, power supply, transmit and receive system electronics, but uses a higher performance gradient coil. The 3T UHP system is not FDA approved, and is subject to the 21 CFR 812 investigational device(IDE) regulations as well as 21 CFR 50 and 56. The system has been tested by GE according to UL606001-1 and also for compliance with IEC 60601-2-33 (ed 3.1) -- meeting limits and guidelines for peripheral nerve stimulation, patient thermal, SAR limit, acoustic noise, flammability rating UL94-5VA for safety covers, hydrostatic pressure, electrical hazards, dielectric strength and pinch point. The MRI scans in this study will also utilize operational parameters within FDA guidelines for Nonsignificant Risk thus an Investigational Device Exemption (IDE) from FDA should not be necessary. In addition, the MR research being conducted requires highly specialized software that does not exist in the clinical MR market, so it is designed and implemented by researchers at the CNI. Any such software will be considered investigational, will function as a non-significant risk device, and is subject to the 21 CFR 812 investigational device (IDE) regulations as well as 21 CFR 50 and 56. The investigational image acquisition software will conform to FDA guidelines for MR safety related to heating (SAR), peripheral nerve stimulation (dB/dt), and acoustic noise.

